## 10. Study Withdrawal/Discontinuation

Subjects will be informed that they can discontinue or withhold participation at any time for any reason. Subjects will be compensated for their time and participation.

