### **Manipulating sensory feedback from gut to influence nutrient metabolism**

Sensory feedback to the brain is based on the chemical milieu of the lumen and the distension status of the gut wall. Distension and contraction of the wall relay sensory signals of nutrient entry. This rhythmic contraction of the gut wall is the consequence of neurotransmission at presynaptic motor terminals, largely mediated by release of acetylcholine (Ach). Blocking this neurotransmission would prevent contraction of the smooth muscle wall and potentially relay a false sensory signal of nutrient entry and/or satiety.

Botulinum neurotoxins (BoNT), are some of the most potent anti-cholinergic agents that reduce muscle contraction. The most potent serotype A (available commercially as BOTOX®) has now been approved by the FDA for treatment of several neuromuscular conditions including blepharospasm, spasm, dystonia, spasticity, and even cerebral palsy in children. Botox possesses several unique pharmacological properties – it is specific, very potent, has limited diffusion from the injection site and is reversible. Based on its properties and evidence-based results, we propose to explore actions of Botox on the intestinal smooth muscle wall and its possible use in manipulating sensory feedback. If proved to be successful, this approach could provide a new treatment paradigm for T2D and metabolic diseases with or without obesity. This potential application of the drug has never been explored.

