**Strabismus:**

Strabismus patients receiving higher doses of BOTOX reported vertical deviation. About 17% of 2058 adults that received a total of 3650 injections for treatment of horizontal strabismus reported vertical deviation. Ptosis was reported in 1%, 16%, and 38% after injections in inferior rectus, horizontal rectus, and superior rectus, respectively. Retro bulbar hemorrhage was reported in 0.3% cases.

In general, local muscle weakness appears to be the most commonly reported and expected event following BOTOX injection in muscles. However, weakness of adjacent muscle tissues, and rarely remote tissues occurring as a result of “spread of toxin effect” have been reported in adult and pediatric patients as well. Events typically observed after any injection procedure including localized pain, inflammation, tenderness, bruising, erythema, and needle-related pain or anxiety have been reported in some clinical trials.

We will recruit obese subjects with pre-diabetes or T2D for the proposed clinical study for 5 visits. After informed written consent is obtained, subjects will be admitted to the Clinical Research Center (CRC), and will undergo upper endoscopic injection of Botox into the duodenal wall. We anticipate that injections of Botox into the duodenal wall will result in significant weight loss and improvements in glucose tolerance and duodenal nutrient sensitivity. Subjects will be studied over a period of 6 months. Subjects will be asked to complete 5 study visits: On the first visit, each subject will undergo an oral glucose tolerance test (OGTT). At visit 2, subjects will undergo an esophagogastroduodenoscopy (EGD) procedure for the delivery of BtX-A to the duodenal wall. Visits 3-5 will be made 1, 3, and 6 months after EGD (Figure 1). On every study visit, body weight and body composition will be recorded and oral glucose tolerance test (OGTT) be performed. Nutrient sensing test will be performed at visits 1 and 3.

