## 5. Screening and Enrollment

Obese subjects ( $\text{BMI} \geq 30 \text{ kg/m}^2$ ) with prediabetes or type 2 diabetes ( $n = 20$ ) will be recruited by solicitation flyers, recruitment emails using Research Match and LISTSERV that reaches all Vanderbilt employees, residents, and students, and Facebook advertisements. Subjects who do not qualify for bariatric surgery, or subjects who are awaiting insurance approval for a bariatric procedure at the Center of Surgical Weight Loss, One Hundred Oaks (OHO) at Vanderbilt University Medical Center will also be contacted via emails and telephone calls.

Subjects will undergo an initial screen by the study coordinator or research staff to assess eligibility and ability to comply with the study requirements. Prior to each study visit, subjects on oral anti-diabetic medications will be asked to discontinue these medications 4 days prior to their study visit. Diabetic subjects will be instructed to monitor their pre-prandial blood glucose during this time and to contact the study physician if their blood glucose levels are greater than 250 mg/dL for two consecutive readings. The study physician may instruct the subject to initiate short-term insulin therapy or resume their oral anti-diabetic medications; in either case the subject will be excluded from the study. Subjects will be instructed to maintain their usual diet and physical activity levels for 1 week prior to each study visit and to arrive fasted for every visit (only water after dinner).

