### 8.2. Protections against risk

(a) Minimizing physical, psychological, and social risks. Participation in this study is completely voluntary. Subjects will be free to drop out of the study due to any issues related, but not limited to physical discomfort, pain or other adverse events (AEs). Screening will be performed by a physician or nurse staff to ensure appropriate selection criteria are employed. Subjects will be free to refuse to respond to any question that may result in psychological disturbance. All patient care information utilized will be confidential and anonymous.

(b) Minimizing risks to confidentiality.

- All records and data will be de-identified and securely stored in Vanderbilt’s HIPAA-compliant, password protected data base, REDCap®; this is a secure web application for collection and management of clinical trial data developed by Vanderbilt University in collaboration with a vast consortium of thousands of active institutional partners.
- The subject’s identification is concealed, and a number is used as the identifier instead of the name. Only the PI, co-investigator, and research assistant will have access to identifiable private information. The PI will be responsible for maintaining the repository

and the identity of the samples. De-identified specimens will be released by the PI to projects after IRB approval only. Any paper documents will be stored in the PI's locked officer. All research samples (serum and plasma) obtained will be de-identified and stored in our locked freezers for an unlimited period of time. Only research personnel associated in our laboratory who are directly involved with the study will have access to research samples.

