## 11. Statistical Analyses

Sample Size: We hypothesize that Botox will reduce body weight, improve glucose tolerance, and augment lipid sensing during fasting and post-prandially, in Class I-III obese subjects. Our outcome measures for the effects of Botox are: body weight; area under the curve (AUC) for plasma levels of ghrelin, CCK, GIP, and GLP-1; and glucose AUC. Power calculation based on previous studies was performed using nQuery Advisor software. The number of subjects needed to detect a 15% decrease in body weight ( $n=16$ ), 10-15% decrease in plasma levels of gut peptides ( $n=14-16$ ), and a 10% decrease in glucose AUC ( $n=16$ ) was determined for an estimated 90% power (two-sided type I error rate = 0.05), with effect size of 0.25. We anticipate studying 20 subjects to account for attrition.

Statistical Analysis Plan: We will analyze pre- and post-intervention measurements at 1, 3, and 6 months using one-way repeated measures ANOVA for each outcome. Correlation between visits will be determined by the first-order autoregressive (AR1) rule which assumes that correlation among repeated measures decline exponentially with time. We will also determine the most optimal (1, 3, or 6 months) and inter time point differences for each outcome.

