## 12. Anticipated Results, Potential Pitfalls

Based on our preliminary data in mice, and assuming overlapping phenotype in humans, we anticipate that at least 60% of obese subjects recruited will lose 10-15% body weight within the first 6 months. We also anticipate at least 10% decrease in blood glucose AUC as early as 1 month after injections, which will sustain until 6 months, or as long as the actions of Botox last in human GI smooth muscle. We are aware of potential dose-dependent effects of Botox and this will be followed up in future trials. Furthermore, sustained improvements in glucose tolerance, if observed, may be a weight loss dependent effect, and dissecting out weight-independent effects will be explored in future trials as well.

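### Injected subjects who leave have no scheduled weight or safety contact afterwards, and Section 11 does not say how their missing visits enter the analysis

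*Combined protocol and SAP*

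**What the plan says.** The intervention is given once. The end of Section 3.2 states: "At visit 2, subjects will undergo an esophagogastroduodenoscopy (EGD) procedure for the delivery of BtX-A to the duodenal wall". No repeat injection is described. Follow-up visits are at 1, 3 and 6 months.

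Section 10 consists of a right-to-withdraw sentence, "Subjects will be informed that they can discontinue or withhold participation at any time for any reason", and a sentence on compensation. Section 8.2 adds that subjects are "free to drop out of the study due to any issues related, but not limited to physical discomfort, pain or other adverse events". Section 5 provides for removal by the study: if high glucose before a study visit leads to insulin or to resumed oral medication, "in either case the subject will be excluded from the study". Because that rule applies ahead of every visit, it can operate after the injection as well as before it. None of these passages says what is collected from a subject who has left.

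Section 11 sets n = 16 for body weight and then says "We anticipate studying 20 subjects to account for attrition". It plans a one-way repeated measures ANOVA with AR(1) correlation, and names no analysis population and no method for missing visits. Section 12 gives an expectation over everyone recruited: "we anticipate that at least 60% of obese subjects recruited will lose 10-15% body weight within the first 6 months".

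**The concern.** In a trial of repeated dosing, withdrawal usually ends both exposure and observation. Here it can end only observation: the toxin has been delivered and its effect runs its course whether or not the subject attends.

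Those with side effects or no weight loss are plausibly the likeliest to stop attending, and Section 8.2 foresees departures for harm. In a randomised trial a control arm would show some of this loss. Here the result is a change from baseline in one group, so selective departure feeds directly into the estimate.

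On safety, the fixed contacts after discharge are nurse calls on days 1 and 7, a telephone visit at one week, and visits 3 to 5. A subject who leaves after the first week misses all the remaining fixed contacts. What was never collected cannot be recovered at analysis, so this goes beyond missing wording in the analysis plan.

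**Working it through.** **1. The plan's own figures.** Inputs from Section 11: 90% power, two-sided 0.05, effect size 0.25, n = 16, 20 enrolled. There are four time points (baseline, 1, 3 and 6 months). The scale of the effect size is not defined. Taking it as the variance of the means over the within-subject error variance (an assumption), the noncentrality is 16 × 4 × 0.25 = 16 with 3 and 45 degrees of freedom. Power is then 91.0%, and 16 is the smallest n that reaches 90%. So n = 16 reproduces on that reading.

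For attrition, 16 / (1 − 0.20) = 20. No dropout rate is stated, but 20 enrolled for 16 needed allows for 20 − 16 = 4 losses, or 20%. The sample size is not in dispute; it supplies the 4 used below.

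**2. Effect on mean weight loss.** With k leavers of 20, completer mean C and leaver mean L, the mean over all injected is [(20 − k) × C + k × L] / 20. C = 8.0% is assumed, L is assumed, and all 20 are taken to be injected with every departure afterwards.

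| k | L | All injected | Completers / all injected |
|---|---|---|---|
| 4 | 0% | (16 × 8.0 + 4 × 0)/20 = 6.4% | 8.0/6.4 = 1.25 |
| 4 | 4% | (128 + 16)/20 = 7.2% | 8.0/7.2 = 1.11 |
| 2 | 0% | (18 × 8.0 + 2 × 0)/20 = 7.2% | 1.11 |
| 4 | 8% | (128 + 32)/20 = 8.0% | 1.00 |
| 4 | 12% | (128 + 48)/20 = 8.8% | 8.0/8.8 = 0.91 |

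The first row is the planned loss with no benefit in any leaver; its ratio is simply 20/16. The last row shows that the direction is not guaranteed: someone who leaves because of a gastrointestinal effect might have lost more weight than those who stay.

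**3. Effect on the proportion expected to respond.** Sixty per cent of 20 is 12. If 10 of 16 completers lose at least 10% and no leaver did, the figure is 10/16 = 62.5% on completers and 10/20 = 50% on all injected. If 12 respond and four non-responders leave, it is 12/16 = 75% against 12/20 = 60%.

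**4. Effect on safety, extreme case.** Suppose four leavers each have an event that arises after leaving and is never learned of. The report would show 0 of 16 (95% CI 0 to 20.6%), or 0 of 20 (0 to 16.8%) if they stay in the denominator. The truth would be 4 of 20, or 20% (5.7 to 43.7%).

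**5. What the analysis would do with leavers.** A classical repeated measures ANOVA omits any subject with a missing visit. A likelihood-based model with AR(1) correlation keeps the visits made before leaving, but remains biased if leaving depends on weights that were never measured. Section 11 fits either description. Only collecting the later weights addresses the second problem.

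**The case against.** A reader might infer that withdrawal ends all data collection. The documents do not say so: Section 10 is silent on what follows, and the consent form, which may carry terms on withdrawal, is not among the reviewed text.

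A reader might also infer that leavers vanish from the safety record. Nothing removes events already recorded. Section 9 sends an annual summary of all adverse events to the IRB and NIH, the nurse may call as needed, and the 24/7 number stays open. Section 3.2 says reactions generally occur in the first week, when the scheduled calls fall. This stands in part. But that statement concerns approved uses elsewhere in the body, and Section 1 says the present use has never been explored. In the protocol's mice, gut distension and apparent dysmotility persisted to 6 weeks. In the overactive bladder data, urinary tract infection is 18% within 12 weeks and 26% over the whole study. The open line depends on the subject calling.

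Nor does Section 11 specify a completer-only analysis; its AR(1) structure is compatible with a model that keeps earlier visits. The 60% in Section 12 is an expectation, with no decision attached, so meeting or missing it has no formal consequence. A leaver who had already lost 10% at month 1 or 3 would satisfy its wording.

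The effect should not be read as permanent. Section 1 says the drug "and is reversible", and the mouse effects had almost gone by 10 weeks. What cannot be stopped by leaving is exposure to the dose already given.

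Section 13 has real retention measures: flexible scheduling, tracking through additional contacts, and payments. They aim to prevent loss and do not say what is collected when it happens.

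**Conclusion.** The point holds as a cheap improvement. Following the plan as written yields no scheduled weight or safety data on an injected subject once that subject leaves, in an uncontrolled study of 20 that allows for about 4 losses and states no missing-data method.

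Under the least favourable of the simple assumptions (four leavers, all after injection, none having lost weight), mean loss would be overstated by a quarter: 8.0% against 6.4%. With two such leavers, or four who lost half as much as completers, the overstatement is about 11%. If leavers resemble completers it is nil. Any attrition in the interval of up to two weeks between visit 1 and the injection reduces the number affected. These are illustrations of possible size, not predictions, because the documents give neither a dropout rate nor any outcome for leavers.

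**What to change.** **Section 10.** Separate stopping study visits from withdrawing consent for contact. For an injected subject who stops visits but allows contact, record the reason and obtain a weight at that time. At each remaining 1-, 3- or 6-month time point, make an adverse event call and obtain a clinic or home-scale weight. Apply the same collection to subjects excluded after injection under Section 5; this concerns data only and leaves the clinical rule there untouched.

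**Section 11.** Analyse all injected subjects with every available visit, using a likelihood-based repeated measures model with the planned AR(1) structure. Add a sensitivity analysis that sets leavers to their baseline weight.

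**Section 12.** If the 60% expectation is reported, use all injected subjects as the denominator. Count as reaching it any subject with a recorded loss of at least 10% at any visit within 6 months, and all others as not reaching it.

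**Cost.** Consent and protocol wording and a few telephone calls, using contact details that Section 13 already gathers. The sample size does not change. The reported weight result may be less favourable.

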## 11. Statistical Analyses

Sample Size: We hypothesize that Botox will reduce body weight, improve glucose tolerance, and augment lipid sensing during fasting and post-prandially, in Class I-III obese subjects. Our outcome measures for the effects of Botox are: body weight; area under the curve (AUC) for plasma levels of ghrelin, CCK, GIP, and GLP-1; and glucose AUC. Power calculation based on previous studies was performed using nQuery Advisor software. The number of subjects needed to detect a 15% decrease in body weight ( $n=16$ ), 10-15% decrease in plasma levels of gut peptides ( $n=14-16$ ), and a 10% decrease in glucose AUC ( $n=16$ ) was determined for an estimated 90% power (two-sided type I error rate = 0.05), with effect size of 0.25. We anticipate studying 20 subjects to account for attrition.

Statistical Analysis Plan: We will analyze pre- and post-intervention measurements at 1, 3, and 6 months using one-way repeated measures ANOVA for each outcome. Correlation between visits will be determined by the first-order autoregressive (AR1) rule which assumes that correlation among repeated measures decline exponentially with time. We will also determine the most optimal (1, 3, or 6 months) and inter time point differences for each outcome.

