## Study visit 2 (within 2 weeks after the first visit):

- Subjects will undergo esophagogastroduodenoscopy (EGD) procedure for the delivery of BOTOX to the duodenal wall, to be performed by [name] at the Vanderbilt Gastrointestinal Endoscopy Suite (VGIES). We have been exempted from Investigational New Drug (IND) regulation for the proposed testing by the FDA (letter attached).
- Subjects will be monitored in the VGIES for 30 minutes and discharged with instructions for follow-up and contact information of the physicians' team (Drs. [name], [name]).

**Telemedicine visit** (1 week after SV2): Study team member will contact subject by telephone to assess if there have been any adverse events from the study procedures completed thus far.

**Study Visits 3-5** (1, 3, and 6 months after EGD): On every study visit, body weight, body composition via DEXA, food intake, and feeding behavior will be recorded and post-absorptive OGTT will be performed. Nutrient sensing test will be repeated at visit 3.

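### Section 11 does not say whether subjects who miss a visit stay in the weight and glucose AUC analyses, and the named ANOVA, read literally, drops them

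*Combined protocol and SAP*

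**What the plan says.** Section 11 (Statistical Analyses) gives the analysis in two sentences. The first is "We will analyze pre- and post-intervention measurements at 1, 3, and 6 months using one-way repeated measures ANOVA for each outcome". The second is "Correlation between visits will be determined by the first-order autoregressive (AR1) rule which assumes that correlation among repeated measures decline exponentially with time".

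The sample-size paragraph of the same section asks for 16 subjects for body weight and 16 for glucose AUC. That number "was determined for an estimated 90% power (two-sided type I error rate = 0.05), with effect size of 0.25". It then adds "We anticipate studying 20 subjects to account for attrition", without an attrition rate.

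Section 6 sets the visits. At 1, 3 and 6 months, "On every study visit, body weight, body composition via DEXA, food intake, and feeding behavior will be recorded", and an OGTT is done. The nutrient sensing test, which supplies the gut hormones, is done only at visits 1 and 3, that is, at baseline and 1 month.

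On loss of subjects:
- Section 10 says "Subjects will be informed that they can discontinue or withhold participation at any time for any reason" and does not mention data already recorded.
- Section 5 excludes subjects who, while off oral medication before a visit, have repeated high glucose readings and are told to start insulin or resume their drugs.
- Section 13 addresses attrition through retention measures only.

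No section defines an analysis set, a rule for missed visits or a sensitivity analysis.

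**The concern.** Classical repeated measures ANOVA works on complete rows. A subject seen at baseline, 1 and 3 months who misses month 6 leaves every comparison, including the 1-month one for which the data exist. Section 12 expects a glucose effect as early as 1 month, and in the mice of Section 3.1 the effect lasted at least 7 weeks and was almost reversed by week 10. The 1-month values are therefore ones the trial can ill afford to lose.

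Two things are at stake. One is information: partial records are thrown away in a trial of 20. The other is bias: if those who leave had responded poorly, the completers' mean overstates the effect, and there is no control arm against which to see this. For glucose AUC, one outcome-related route out is written into the plan, namely the Section 5 exclusion.

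**Working it through.** **1. The plan's own figure.** Inputs from Section 11: alpha 0.05, power 90%, effect size 0.25, four time points. The scale of 0.25 is not defined. Read it as variance of the means divided by SD²(1−ρ) and assume sphericity. The noncentrality is then n × 4 × 0.25 = n, with 3 and 3(n−1) degrees of freedom.
- n = 15: power 0.888
- n = 16: power 0.910
- n = 20: power 0.965

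So 16 is reproduced. Enrolment follows from 16 / (1 − 0.20) = 20, an implied attrition of 20%.

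**2. Recorded data lost under a complete-row rule.** Planned weights: 20 × 4 = 80. If 4 subjects leave after month 1, 4 × 2 = 8 recorded weights (baseline and month 1) go unused. If they leave after month 3, 4 × 3 = 12 go unused.

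**3. How many rows are complete.** Suppose each follow-up visit is missed independently with probability p (assumed). Expected complete subjects are 20(1−p)³.
- p = 5%: 20 × 0.857 = 17.1
- p = 10%: 20 × 0.729 = 14.6

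The count falls below 16 once p exceeds 1 − 0.80^(1/3) = 7.2%. The 10% case means 27% incomplete subjects, more than the 20% the plan implies.

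**4. Possible bias in 6-month weight change.** The documents give no SD, correlation or dropout mechanism, so all of these are assumed: true mean change −3, −7 and −10% at 1, 3 and 6 months; SDs 3, 5 and 6 points; AR(1) correlation 0.5 or 0.8; 20 subjects, 4 of whom leave; 1,000 simulated trials per case. The likelihood model is a multivariate normal with unstructured covariance fitted to all recorded changes from baseline.

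| Who leaves | Completers (ρ 0.5 / 0.8) | Likelihood, all visits (ρ 0.5 / 0.8) |
|---|---|---|
| Unrelated to response | −10.0 / −10.0 | −10.0 / −10.0 |
| Depends on recorded weights | −10.8 / −11.3 | −10.0 / −10.0 |
| Depends on unrecorded weights | −11.5 / −11.7 | −11.3 / −10.8 |
| Poor responders, before any follow-up visit | −11.7 / −11.7 | −11.7 / −11.7 |

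The spread of single-trial estimates is about 1.5 points, so the simulation error of each mean is about 1.5/√1000 = 0.05.

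**5. Milder dropout.** Assume 17% leave after month 1, with a logit slope of 0.5 to 2 per SD of the recorded 1-month change, a correlation of 0.3 to 0.7 between months 1 and 6, and a 6-month SD of 4 to 6 points. The completers' bias is (shift in the completers' mean 1-month change, in SDs) × correlation × SD. It runs from 0.1 to 1.0 points.

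**6. Gut hormones.** With baseline and 1 month only, a missed 3- or 6-month visit removes nobody, and the subjects with a baseline and a follow-up value are exactly the complete pairs.

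**The case against.** The strongest reply is the AR(1) sentence. Classical repeated measures ANOVA has no AR(1) option. A model with AR(1) errors is normally fitted by likelihood or generalised least squares, and such a fit can use partial records. A reader might infer from the ANOVA label that the plan deletes every subject who misses a visit. The documents do not say so, and deletion follows only from the method's usual form. Nor do they say the opposite: the label and the correlation sentence point to different analyses, and an analyst could follow either. That ambiguity stands.

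The inflation from 16 to 20 does not settle it. A mixed-model plan would inflate in the same way, and the documents never speak of completers.

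A reader might also infer that the reported weight loss will be exaggerated. Nothing in the documents says that poor responders leave. Treatment is a single session, visits are paid with a completion bonus, and retention is planned. The only outcome-related removal in writing concerns glucose. The bias is therefore a possibility and may be nil.

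Finally, a mixed model might be taken as a full cure. The last two rows of the table show that it is not.

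It is fair to add that this is a 20-subject pilot. That limits how much the point matters, but the change costs little.

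**Conclusion.** The point holds for body weight and glucose AUC. For these outcomes Section 11 names a method that in its classical form needs complete rows, allows for about 20% attrition, and does not say that partial records are used. On the literal reading, 8 to 12 of 80 planned weights would be recorded and then ignored if four subjects left after month 1 or month 3.

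The overstatement of 6-month weight loss lies between about 0 and 2 percentage points. It is zero if dropout is unrelated to response, and 1.7 points is the largest value in the cases tried. This range rests wholly on assumed means, SDs, correlations and dropout patterns. No figure can be given for glucose AUC, because the documents give no variability for it.

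A shortfall below 16 complete subjects should not be inferred either: at 5% missed per visit 17.1 are expected, and the 14.6 at 10% requires more loss than the plan allows for.

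The sample size is not in question. This should be put right before the data are analysed, but it does not undermine the design.

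**What to change.** In Section 11, replace the ANOVA for body weight and glucose AUC with a linear mixed model fitted by REML:
- visit (baseline, 1, 3, 6 months) as a categorical factor;
- a stated covariance structure, either AR(1) with its time scale defined or unstructured;
- Kenward-Roger degrees of freedom;
- all recorded visits of all injected subjects;
- contrasts of each follow-up visit against baseline.

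Add a table of missed visits by time point with reasons, listing separately the subjects excluded under the glucose rule in Section 5.

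Add a sensitivity analysis for outcome-related dropout. One option is to make the unrecorded changes progressively less favourable than the model predicts, down to no change from baseline, and to include subjects with no post-baseline visit, for whom the mixed model cannot help. A completer analysis alone would not serve this purpose.

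The gut-hormone comparison of baseline with 1 month needs no change on this account.

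The cost is a few lines of SAP text and slightly more analysis work; enrolment stays at 20. The main estimate would rest on dropout being explained by recorded values (missing at random), which is a weaker assumption than the one a completer analysis makes.

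### Section 11 tests six outcomes as equals at 0.05 with no primary outcome or visit, and picks the best month from the data for the two outcomes measured at all three follow-ups.

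*Combined protocol and SAP*

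**What the plan says.** Section 11 lists the outcome measures without ranking them: "body weight; area under the curve (AUC) for plasma levels of ghrelin, CCK, GIP, and GLP-1; and glucose AUC". That makes six. The sample size is worked out separately for weight, gut peptides and glucose AUC, each at "estimated 90% power (two-sided type I error rate = 0.05), with effect size of 0.25". The analysis is stated as: "We will analyze pre- and post-intervention measurements at 1, 3, and 6 months using one-way repeated measures ANOVA for each outcome". The next step on timing is: "We will also determine the most optimal (1, 3, or 6 months) and inter time point differences for each outcome".

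No other section fills the gap. Section 2 numbers three aims, with body weight first, but calls none of them primary. Section 12 gives expectations (weight loss inside the first six months, a glucose AUC fall from month 1), not a designated endpoint. No testing order or multiplicity adjustment appears anywhere.

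The visit schedule matters here. Section 6, and the study outline at the end of Section 3.2, place weight and the OGTT at 1, 3 and 6 months. They place the nutrient sensing test, which supplies the hormone AUCs, only at visits 1 and 3, that is, at baseline and 1 month.

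**The concern.** There are two separate problems. First, with six equal outcomes and no stated criterion for success, any one significant result could be presented as evidence of an effect, and nothing in the plan limits how often that happens by chance. Second, choosing a month by looking at the results favours the month in which random error happened to help, so the effect quoted for that month tends to be too large. The plan describes no control arm, so no comparator would expose a chance fall at the chosen month. An effect estimate inflated in this way would mislead anyone who used it to size later work.

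**Working it through.** **Inputs from the plan.** Six outcomes; two-sided alpha 0.05; 90% power; effect size 0.25 (not defined); 16 subjects for weight and for glucose AUC, 14-16 for gut peptides; 20 enrolled (all Section 11). Follow-up times: three for weight and glucose AUC, one for each hormone (Section 6).

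**Assumptions.** AR(1) correlation between successive visits of 0.3 to 0.9 (the plan gives the structure but no value); correlation between outcomes of 0 to 0.5; 16 completers.

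**1. The plan's own figure.** Take 0.25 as the variance of the time means divided by σ²(1−ρ). With m = 4 time points, the noncentrality is n × m × 0.25 = 16 × 4 × 0.25 = 16, on 3 and 45 degrees of freedom. Power is 91.0% at n = 16 and 88.8% at n = 15, so 16 is reproduced under this reading. It is the size for one outcome tested alone at 0.05. Applying Bonferroni to six such outcomes (0.05/6 = 0.0083 each) gives 73% power at 16 and 86% at 20, and needs 22 completers for 90%. This treats every outcome as having four time points, so it is only illustrative for the hormones.

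**2. Error across outcomes.** One test per outcome, no true change, independent outcomes: 1 − 0.95⁶ = 0.265. Simulated with 16 subjects, the rate is 26-27% at correlation 0, about 25% at 0.3 and 21-22% at 0.5.

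**3. Contrasts the schedule can supply.** 2 outcomes × 3 visits + 4 outcomes × 1 visit = 10 comparisons with baseline. If each were tested at 0.05: 1 − 0.95¹⁰ = 0.401 if independent, and 31-37% in simulation.

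**4. Error across visits within one outcome.** For weight or glucose AUC, test each of the three changes from baseline at 0.05 and count any significant one. The simulated error is about 11-12% (10-13% across all settings), against 5%. This applies only if the visit tests are run whether or not the overall ANOVA is significant.

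**5. Bias from choosing the month.** With no true change, the mean of the largest of the three falls, in units of the between-subject SD σ, is about 0.19, 0.16, 0.13 and 0.08 for ρ = 0.3, 0.5, 0.7 and 0.9. The SD of the one-month change is σ√(2(1−ρ)) = 1.18σ, 1.00σ, 0.77σ and 0.45σ. The ratio is 0.16-0.17 throughout.

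To put this in weight units, assume the one-month change has an SD of 5 percentage points: 0.16 × 5 = 0.8 points. The bias depends on the true pattern over months. Illustrative patterns, same SD and n:

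| True change at 1 / 3 / 6 months (%) | Overstatement of the chosen month (points) |
|---|---|
| equal at all three | about 0.8 |
| −5 / −10 / −10 | about 0.5 |
| −10 / −12 / −10 | under 0.3 |
| −8 / −12 / −6 | about 0 |

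**The case against.** The strongest reply is that this is a pilot (the data safety monitoring plan in Section 9 says so), with three distinct aims and no rule that any single significant outcome counts as success. Describing when the effect peaks is a sensible aim when its duration in human gut muscle is unknown, and the same sentence also commits to the differences between time points, so the other months are not ignored. Nothing says that the best month becomes the headline result. The bias is also small beside the 15% weight loss for which the trial is sized: 0.8/15 is about 5%.

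Much of this stands as a limit on size. It does not remove the point. Section 11 claims 90% power at two-sided 0.05 and Section 13 speaks of keeping power to detect a true effect, so the results are set up as tests. A pilot label does not remove selection bias from an estimate.

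A reader might infer several stronger things that the documents do not support:

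- That there are 6 × 3 = 18 tests, with an error of 1 − 0.95¹⁸ = 60%, or that a best month is chosen for all six outcomes. Section 11's wording invites this, but the hormones have one follow-up visit.
- That the 11-12% error is certain. The named test is one ANOVA per outcome. If visit comparisons follow only a significant and valid overall test, the error for each outcome stays near 5%. The plan does not say which applies.
- That 0.8 points is the expected bias. It is the equal-months case under an assumed SD.
- That 6 months is the plan's implied primary visit. Section 12 says within six months, not at six months, and Section 3.1 reports that the mouse effect had almost reversed by 10 weeks.

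**Conclusion.** The point holds in two parts. The first covers all six outcomes: with no primary outcome and no adjustment, the chance of at least one false positive is about 26% if they are independent and 21-22% at correlation 0.5, assuming one test per outcome at 0.05 and that a reader would credit any one of them. Gating the visit comparisons does not change this.

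The second covers body weight and glucose AUC only, and it is conditional. If the chosen month's effect is reported, it is biased away from zero by at most about 0.16-0.17 SD of the one-month change at 16 completers, falling to little or nothing when one month is clearly best. If visit tests are ungated, the error for each of these two outcomes is about 11-12%. The sponsor should correct this before data are seen. It does not invalidate the design.

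**What to change.** Amend Section 11 before any outcome data are seen:

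- Name body weight (Aim 1) as the single primary outcome, with one pre-specified test at two-sided 0.05. This can be the overall repeated-measures test across visits, or the change from baseline at one visit that the sponsor names and justifies against the expected duration of effect.
- Make glucose AUC and the four hormone AUCs secondary, either Holm-adjusted or reported with 95% confidence intervals and no claim of success.
- Replace the search for the best month with reporting of all 1-, 3- and 6-month changes, with confidence intervals, for body weight and glucose AUC, and of the 1-month change for the hormones. Label any statement about peak timing exploratory.
- Reconcile the wording that applies the month comparison to every outcome with the hormone sampling schedule in Section 6.

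The cost is a few sentences, with no added subjects, visits or assays. With 16 completers, a single paired test keeps the error at 5% and has 90% power for a mean change of 0.87 SD. For a 15% weight loss, that allows an SD of change up to about 15/0.87 = 17 percentage points. The downside is that success can be claimed only on the pre-named outcome. If a single visit is chosen, an effect confined to another visit would be reported but could not carry the claim.
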